#### **6.4.1.1. Incidence of Adverse Events**

An overall summary including the number and percentage of participants who experience the following will be presented:

- Any unsolicited AEs, defined as SAEs, MAAEs, AESIs, and AEs leading to withdrawal IP and study participation
- Any SAEs
- Any MAAEs
- Any AESIs
- Any unsolicited AEs leading to discontinuation from study vaccine
- Any unsolicited AEs leading to discontinuation from participation in the study

The table will also include number and percentage of participants with unsolicited AEs that are treatment-related in each of the above categories by injection stage.

In addition, separate listings containing individual participant AE data for serious AEs, MAAEs, AESIs, and unsolicited AE leading to discontinuation from study vaccine and unsolicited AEs leading to discontinuation from participation in the study will be provided separately.

#### **6.4.1.2. AEs by System Organ Class and Preferred Term**

The following summary tables of AEs will be provided by SOC and PT using frequency counts and percentages (i.e., number and percentage of participants with an event):

- All SAEs and all SAEs that are treatment-related
- All MAAEs and all MAAEs that are treatment-related
- All AESIs and all AESIs that are treatment-related
- All unsolicited AEs leading to discontinuation from study vaccine and all unsolicited AEs leading to discontinuation from study vaccine that are treatment-related
- All unsolicited AEs leading to discontinuation from participation in the study and all unsolicited AEs leading to discontinuation from participation in the study that are treatment-related

- All unsolicited AEs, defined as SAEs, MAAEs, AESIs, and AEs leading to withdrawal IP and study participation, and all unsolicited AEs that are treatment-related

#### **6.4.1.3. AEs by System Organ Class, Preferred Term and Severity**

All AEs will be provided by SOC, PT, and severity by CTCAE grade 1 - 3 (mild, moderate, and severe) using frequency counts and percentages. The same analysis will be repeated for all AEs that are treatment-related. SAEs, MAAEs, AESIs, all unsolicited AEs leading to discontinuation from study vaccine, and all unsolicited AEs leading to discontinuation from participation in the study will be analyzed in a similar fashion with all treatment-related versions analyzed as well. PT will be displayed in descending order of frequency based on the Any column (as opposed to Related column) of mRNA-1273.712.

Any unsolicited AEs reported for participants with elevated troponin may be summarized by severity, along with any treatment-related AEs for these participants.

#### **6.4.1.4. Myocarditis, Pericarditis, Myopericarditis, and Cardiomyopathy**

Myocarditis, pericarditis, and myopericarditis will be summarized as per a customized MedDRA query (CMQ) based on PTs in the Center for Disease Control (CDC) case definition of myocarditis, pericarditis, and myopericarditis at the following time intervals: up to 14 days after any injection, up to 14 days after injection 1, and up to 14 days after injection 2. Cardiomyopathy and non-infectious myocarditis, pericarditis, and myopericarditis will also be summarized at the same time intervals. Results will be presented by PT. A listing of suspected cases of myocarditis, pericarditis, and myopericarditis will be provided based on the data adjudicated by the Cardiac Event Adjudication Committee.

#### **6.4.2. Pregnancy Evaluation**

Safety laboratory testing will include pregnancy tests.

A pregnancy test will be performed on all female participants of childbearing potential at the Screening Visit and before each vaccine administration (Day 1, Day 29) via point-of-care urine, and as needed at unscheduled visits (urine or serum pregnancy test based on the Investigator's discretion). A follicle-stimulating hormone (FSH) test may be performed at the Screening Visit (Day 0), as necessary and at the discretion of the investigator, to confirm postmenopausal status. Pregnancy outcomes (FSH, positive/negative) will be listed.

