### 1.3. Schedule of Activities

**Table 1: Schedule of Activities**

Visit Number	1	2	3	4	5
Type of Visit	C	C	C	C	C/EOS
Month Timepoint	M0		M1		M2
Timepoint	D1 a (Screening and Baseline)	D4	D29	D32 b	D57 b
Window Allowance (Days)	-7	-2	+3	-2	±3
Days Since Injection	0	3	28/0	3	28
ICF, demographics, concomitant medications, medical history	X				
Confirm participant meets inclusion/exclusion criteria	X				
Full physical examination c	X				
Vital sign measurements d	X	X	X	X	X
Pregnancy testing e	X		X		
Study injection (including 15-minute postinjection observation period) f	X		X		
Blood collection for cardiac troponin I assessment g	X	X	X	X	X
Recording of SAEs, MAAEs, AESIs, AEs leading to withdrawal h	X	X	X	X	X
Recording of concomitant medications i	X	X	X	X	X
Recording of nonstudy vaccinations	X	X	X	X	X
Review of eDiary j	X	X	X	X	X
Study completion					X

Abbreviations: AE = adverse event; AESI = adverse event of special interest; C = clinic visit; D = day; eDiary = electronic diary; EOS = end of study; ICF = informed consent form; M = month; MAAE = medically attended adverse event; SAE = serious adverse event.

- a. The Screening Visit and Day 1 (injection/baseline) visit should be performed on the same day. If because of extenuating circumstances, Screening and Day 1 visits need to be performed on 2 different days, completion of Informed Consent Form, demographics, concomitant medications, medical history and confirming participant meets inclusion/exclusion criteria must be completed on the same day (Screening), and the remaining study procedures must be done on the same day as the injection (Day 1).
- b. Visit 4 must be scheduled 3 days after Visit 3 (a window of up to -2 days is permitted). EOS Visit must be scheduled 28 days after Visit 3 (a 3-day window is permitted).
- c. Physical examination: A full physical examination, including height and weight, will be performed on Day 1. Symptom-directed physical examinations may be performed at other timepoints at the discretion of the Investigator.
- d. On the day of injection (Day 1 and Day 29), vital signs are to be collected before and after injection.
- e. Pregnancy tests are to be collected before each injection ([Section 8.2.6](#)).

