### 8.3.9. **Pregnancy**

- Any participant who becomes pregnant while participating in the study may continue study participation.
- Details of all pregnancies in participants will be collected after the start of study intervention and until 28 days following the last injection. Participants who become pregnant at any time during the study should remain in the study and complete all study visits as scheduled.
- If a pregnancy is reported, the Investigator will record pregnancy information on the appropriate form and submit it to the Sponsor within 24 hours of learning of the participant's pregnancy (see [Section 10.3.2](#)).
- While pregnancy itself is not considered to be an AE or SAE, any pregnancy complication or elective termination of a pregnancy for medical reasons will be reported as an AE or SAE.
- Abnormal pregnancy outcomes (eg, spontaneous abortion, fetal death, stillbirth, congenital anomalies, ectopic pregnancy) are considered SAEs and will be reported as such (refer to [Section 8.3.7](#)).
- The participant will be followed to determine the outcome of the pregnancy. The Investigator will collect follow-up information on the participant and the neonate and the information will be forwarded to the Sponsor.
- Any poststudy pregnancy-related SAE considered reasonably related to the study intervention by the Investigator will be reported to the Sponsor as described in [Section 8.3.7](#). While the Investigator is not obligated to actively seek this information in former study participants, they may learn of an SAE through spontaneous reporting.

Prior to continuation of study intervention following pregnancy, the following must occur:

- The Sponsor and the relevant IRB/IEC give written approval.
- The participant gives signed informed consent.
- The Investigator agrees to monitor the outcome of the pregnancy and the status of the participant and their offspring.

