#### **9.4.2. Safety Analyses**

All safety analyses will be based on the Safety Set.

Safety will include SAEs, MAAEs, AESIs, AEs leading to withdrawal, vital sign measurements, and physical examination findings.

The number and percentage of participants with SAEs, MAAEs, AESIs, and AEs leading to withdrawal will be summarized. These unsolicited AEs will be presented by MedDRA system organ class and preferred term. The unsolicited AEs will be coded according to the MedDRA Dictionary for Adverse Reaction Terminology.

The number of events of SAEs, MAAEs, AESIs, and AEs leading to withdrawal will be reported in summary tables accordingly using descriptive statistics. Pregnancy outcomes will also be summarized.

The safety summaries will be presented by study intervention and injection (ie, post-Injection 1 and pre-Injection 2, and post-Injection 2), and for participants who receive the mRNA-1273.712 for Injection 1 or Injection 2 (ie, post-mRNA-1273.712 injection and throughout the study).

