## 7. Changes from Planned Analyses in Protocol

There are no changes from planned analyses in protocol.

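### SAP 6.4.2 lists FSH and pregnancy-test results as pregnancy outcomes, so the outcome summary planned in protocol 9.4.2 is dropped without being declared

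*SAP*

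**What the plan says.** Protocol 9.4.2, on the safety analyses, states: "Pregnancy outcomes will also be summarized". The data behind that summary are described in protocol 8.2 and 8.3.9. Sites collect details of all pregnancies from the start of study intervention until 28 days after the last injection (8.3.9) or the end of participation (8.2). They send a form to the sponsor within 24 hours of learning of a pregnancy, and "The participant will be followed to determine the outcome of the pregnancy".

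SAP 6.4.2 is the only SAP section that plans an output for pregnancy data. It describes urine tests "at the Screening Visit and before each vaccine administration (Day 1, Day 29) via point-of-care urine", further tests at the investigator's discretion, and an optional FSH test at screening. It then closes with the reporting rule: "Pregnancy outcomes (FSH, positive/negative) will be listed".

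SAP Section 1 says that the SAP takes precedence where its methods differ from the protocol's. SAP Section 7 says: "There are no changes from planned analyses in protocol".

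**The concern.** The SAP uses the protocol's term for something else. A positive or negative test shows whether a participant was pregnant on the day of the test; it does not show how a pregnancy ended. FSH, by the SAP's own account, serves to confirm menopausal status. A programmer following the SAP would build a listing of laboratory results, give it the title of pregnancy outcomes, and produce no summary of pregnancies at all.

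At stake is whether the study report shows what the protocol said it would. All participants are due to receive the vaccine, and participants of childbearing potential are enrolled, so a reader will look for a plain account of how many pregnancies were reported and what became of them. Run as written, the SAP does not supply it, and it tells the reader that nothing has changed.

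**Working it through.** No arithmetic applies: the point depends on no rate, error level or sample size. The check is a comparison of the texts.

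1. **Meaning of outcome.** Protocol 8.3.9 uses the word for the result of a pregnancy: "Abnormal pregnancy outcomes (eg, spontaneous abortion, fetal death, stillbirth, congenital anomalies, ectopic pregnancy) are considered SAEs". SAP 6.4.2 fills the same term with FSH and positive/negative results. Neither is an outcome in the protocol's sense.

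2. **Form of the output.** Protocol 9.4.2 plans one summary. The SAP plans none, only a listing. Both the content and the form have changed.

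3. **Which text governs.** Under SAP Section 1 the SAP prevails, so the protocol's sentence does not survive as a fallback. Protocol Section 9 requires later changes to secondary or exploratory analyses to be listed and explained in the SAP or the study report. Safety is a secondary objective, and SAP Section 7 lists nothing.

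4. **Whether other SAP outputs fill the gap.** Taking the possible cases in turn:

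| Case | Planned display |
|---|---|
| Abnormal outcome, an SAE under protocol 8.3.9 | SAE tables and listings, SAP 6.4.1.1 and 6.4.1.2 |
| Complication, or termination for medical reasons, an AE or SAE under protocol 8.3.9 | AE and SAE tables, same sections |
| Withdrawal because of pregnancy, a recorded reason in protocol 7.2 | Disposition, SAP 6.2.1 |
| Pregnancy with a positive study test | Test listing, SAP 6.4.2, with no outcome |
| Uncomplicated or ongoing pregnancy known only from the pregnancy form | None |

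The last row follows from protocol 8.3.9. Pregnancy in itself is neither an AE nor an SAE there, so the AE tables need not show it. Pregnant participants are also expected to stay in the study, so disposition need not show it either.

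5. **Whether the data exist.** They do in principle, since protocol 8.2 and 8.3.9 require reporting and follow-up. Two limits apply. Protocol 10.3.2 has the forms emailed to the sponsor, and protocol 8.2 warns that information arriving after the end of the study may not enter the clinical database.

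**The case against.** The best case for leaving the SAP alone is that little is lost. The events of most concern already have a display, as the table shows. Participation lasts about two months and contraception is an entry condition through end of study, so reported pregnancies should be few and most would still be ongoing at database lock. Pregnancy is not an endpoint. All of this stands, and it limits how much the point matters. It does not make a test result an outcome, and it does not excuse an undeclared change.

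A reader might infer more than the documents support, in three ways.

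- **That pregnancies after Injection 2 are missed because no test is scheduled then.** It is true that "Pregnancy tests are to be collected before each injection" and that none is scheduled at Day 57. But the protocol does not rely on scheduled tests to find pregnancies. Section 8.3.9 collects all of them until 28 days after the last injection, 8.3 applies the AE collection and reporting rules to them, and 8.2.6 allows a test at any time. The fault lies in what the SAP displays. The test schedule is not part of it.
- **That a share of follow-up left untested, or a number of pregnancies missed, can be stated.** The documents give neither the number of participants of childbearing potential nor a conception rate for them. Any share would depend on whether vaccine follow-up in Sequence 1 is taken to stop at the placebo injection, and protocol 9.4.2 also asks for summaries throughout the study.
- **That the listing would be empty and be misread as showing no pregnancies.** It would hold negative as well as positive results, so the Day 1 and Day 29 tests would fill it.

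**Conclusion.** The inconsistency is real and the SAP is wrong as written on this point. It attaches the name of pregnancy outcomes to FSH and test results, replaces a planned summary with a listing, and declares no change. The consequence is limited to safety reporting: an uncomplicated or ongoing pregnancy recorded only on the pregnancy form has no planned output, and pregnancies that do surface through a test appear without their outcome. The primary cTnI analysis and the cTnI secondary endpoints are unaffected, so this is a minor correction.

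The conclusion rests on reading SAP 6.4.2 as the complete plan for pregnancy data. A table shell outside these documents could already contain the missing summary. In that case the SAP text still needs to be brought into line with it.

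**What to change.** In SAP 6.4.2, replace the closing sentence with two provisions.

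- List the pregnancy-test and FSH results under a title that calls them test results.
- Summarise and list all pregnancies reported through end of study, by intervention sequence and by the injection stages already used in SAP 6.4.1, with the outcome known at database lock. Include categories for ongoing and unknown.

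If the sponsor prefers a listing without a summary, SAP Section 7 should record that as a change from protocol 9.4.2 and give the reason.

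The cost is SAP wording and one small extra output. No new tests or visits are needed. Because the forms are emailed, they may have to be reconciled with the clinical database before the output can be produced; the documents do not show whether the same information is also held there.

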#### **6.4.3. Vital Sign Measurements**

Vital sign measurements, including systolic and diastolic blood pressures, heart rate, respiratory rate, and body temperature, will be presented in a data listing. Vital signs will be graded using the Toxicity Grading Scale for Healthy Adult and Adolescent Volunteers Enrolled in

Preventative Vaccine Clinical Trials ([DHHS 2007](#)). The values meeting the toxicity grading criteria will be flagged in the data listing. The abnormalities meeting the toxicity grading criteria (Grade 2 or higher) in any vital sign measurement will be listed separately. If a participant has a vital sign result with Grade 2 or higher abnormality at any post-injection visit, then all results of vital sign measurement for that participant will be presented in the listing.

Observed values and changes from Day 1 (baseline) for all vital sign measurements will be summarized at each visit (including pre- and post-Injection for Day 1 and Day 29) by intervention sequence. Shift from Day 1 (baseline) in the toxicity grades at each visit and shift from baseline in the toxicity grades to the worst post-baseline result will also be summarized by intervention sequence. These analyses will be repeated using Day 29 as baseline instead of Day 1 to measure the change in vital signs after injection 2. Toxicity grades guidelines can be found in [Table 5 in Appendix F.](#)

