### 6.1. Study Interventions Administered

Participants will receive mRNA-1273.712 and placebo in the study using a crossover design ([Table 4](#)). The mRNA-1273.712 is an mRNA-LNP dispersion consisting of mRNA encoding the S-2P of the SARS-CoV-2 KP.2 subvariant of Omicron, formulated in a mixture of 4 lipids: SM-102, cholesterol, DSPC, and PEG2000-DMG.

Each participant will be administered a CCI  $\mu$ g dose of mRNA-1273.712 and placebo in a crossover design:

- mRNA-1273.712 – placebo sequence: CCI  $\mu$ g of mRNA-1273.712 followed by placebo 28 days later (Sequence 1)
- Placebo – mRNA-1273.712 sequence: placebo followed by CCI  $\mu$ g of mRNA-1273.712 28 days later (Sequence 2)

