## 4. Study Design

### 4.1. Overall Study Design

This is a Phase 4 study designed as a randomized, observer-blind, placebo-controlled, crossover clinical study to assess cTnI levels after vaccination with the KP.2 variant containing messenger ribonucleic acid mRNA-1273.712 Coronavirus disease 2019 (COVID19) vaccine in individuals 12 through 30 years of age. The study will be conducted at clinical study sites across the United States.

Participants will receive study intervention by intramuscular (IM) injection on Day 1. The study will follow a crossover design and the study intervention sequence will be switched on Day 29. Participants will be followed for approximately 1 month after each injection, for a total study duration of approximately 2 months. Safety assessments throughout the study will include SAEs, MAAEs, AESIs, and AEs leading to withdrawal.

Blood samples will be collected from all participants at pre-injection on the day of each injection, as well as at 3 and 28 days after each injection for assessment of cTnI. To aid interpretation of cTnI assessment, participants will record vigorous physical activities in their eDiary for specific periods during the study (i.e., if an elevated cTnI level is detected during the analysis, the activity data for that participant will be reviewed for correlation of vigorous physical activities with elevated cTnI levels) ([Table 4](#)). Depending on when the study injections or end of study (EOS) is scheduled to be completed, the participant will be asked to complete the eDiary for 4 consecutive days post-Injection 1 (Day 1), 4 consecutive days pre- and post-Injection 2 (Day 29), and 4 consecutive days prior to EOS visit (Day 57), and on the day of the EOS visit. Participants will be encouraged, but not required, to avoid vigorous physical activities, when possible, for 4 days

before and after each study injection. Vigorous physical activities refer to activities that take hard physical effort and make you breathe much harder than normal.

The study will be comprised of 5 scheduled in-clinic visits including a combined Screening and Day 1 Visit. Procedures for Screening and injection/baseline should be performed on the same day (Day 1 Visit) but may be performed on 2 separate days if needed due to extenuating circumstances ([Table 3](#)). This study will be conducted in compliance with the protocol, Good Clinical Practice (GCP), and all applicable regulatory requirements.

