### 4.2. Sample Size and Randomization

Approximately 1000 participants will be randomized in a 1:1 ratio to one of 2 intervention sequences (approximately 500 participants in each intervention sequence) in this study, to receive **CCI** µg of mRNA-1273.712 followed by placebo 28 days later (mRNA-1273.712 – placebo [Sequence 1]) or to receive placebo followed by **CCI** µg of mRNA-1273.712 28 days later (placebo – mRNA-1273.712 [Sequence 2]). Approximately 1000 participants will receive **CCI** µg of mRNA-1273.712 for Injection 1 or Injection 2, due to the crossover design. Assuming approximately 10% of participants would be excluded from the mRNA-1273.712 group (Injection 1 or Injection 2) in the Evaluable Set due to any reasons (e.g., early dropout, and major protocol deviations that impact key analysis data), the study has more than 90% probability to observe at least 1 participant receiving mRNA-1273.712 (Injection 1 or Injection 2) with an elevated cTnI at a true rate of 0.3%.

Random assignment of participants will use a centralized interactive response technology (IRT), in accordance with pre-generated randomization schedules.

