**Baseline value**, unless specified otherwise, is defined as the most recent non-missing measurement (scheduled or unscheduled) collected before the first dose of study drug or placebo at Day 1.

**Study day relative to the first injection** will be calculated as below:

- a) Study day prior to the first injection will be calculated as: date of assessment/event – date of the first injection.
- b) Study day on or after the date of the first injection will be calculated as: date of assessment/event – date of the first injection + 1.

**Study day relative to the most recent injection** will be calculated as below:

- a) Study day prior to the first injection will be calculated as: date of assessment/event – date of the first injection.
- b) Study day on or after the date of the first injection but before the second injection (if applicable) will be calculated as: date of assessment/event – date of the first injection + 1.
- c) Study day on or after the date of the second injection will be calculated as: date of assessment/event – date of the second injection + 1.

**Unscheduled visits:** Unscheduled visit measurements will be included in the analyses as follows:

- In scheduled visit windows per specified visit windowing rules in [Appendix B](#).
- In the derivation of baseline/last on-treatment measurements.
- In the derivation of maximum/minimum on-treatment values and maximum/minimum change from baseline values for safety analyses.
- In individual participant data listings.

**Visit window rules:** The analysis visit windows for protocol-defined visits are provided in [Appendix B](#).

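### The Day 1-baseline worst-grade vital-sign shift is not cut at Injection 2, so each sequence column mixes vaccine and placebo periods and no Period 1 worst-grade summary is specified

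*SAP*

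**What the plan says.** SAP 6.4.3 plans three things for vital-sign toxicity grades, all by intervention sequence:

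- A per-visit table: "Shift from Day 1 (baseline) in the toxicity grades at each visit".
- A worst-result table: "shift from baseline in the toxicity grades to the worst post-baseline result will also be summarized by intervention sequence". No end point or injection period is given.
- A second pass: "These analyses will be repeated using Day 29 as baseline instead of Day 1 to measure the change in vital signs after injection 2".

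SAP 6.1 defines baseline as the last non-missing value "collected before the first dose of study drug or placebo at Day 1". SAP 4.1 says that "the study intervention sequence will be switched on Day 29", and Protocol 6.1 that "Participants will receive mRNA-1273.712 and placebo in the study using a crossover design". The vital-sign schedule is the same in both periods: "On the day of injection (Day 1 and Day 29), vital signs are to be collected before and after injection" (Protocol Table 1), with further readings 3 and 28 days after each injection.

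Protocol 9.4.2 counts vital signs as part of safety and presents the safety summaries by intervention and by injection, separating the time between the two injections from the time after the second. SAP section 7 reports no change from the protocol's planned analyses.

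**The concern.** A worst value taken from Day 1 to the end of the study spans the crossover. Sequence 1 contributes a vaccine period then a placebo period, and Sequence 2 the reverse, so both columns describe nearly the same mixture. A Grade 2 reading after placebo falls in the same cell as one after vaccine. A reader comparing the two columns would see near-equality whether or not the vaccine raises the rate of abnormalities, and might take that as a finding.

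Elsewhere the SAP makes the split that is missing here. Adverse events (6.4.1) and concomitant medications (6.2.4) are summarised by injection stage, and myocarditis and pericarditis (6.4.1.4) after each injection separately. The omission in 6.4.3 therefore looks like an oversight.

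**Working it through.** **The plan's own figure.** The documents state no vital-sign figure. Their only sample-size figure is the probability of more than 90% of seeing at least one elevated cTnI at a true rate of 0.3%. With 900 evaluable it is 1 − 0.997^900 = 93.3%, which agrees. It has no bearing on this point.

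**Inputs**

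- Allocation 1:1, about 500 per sequence (SAP 4.2).
- Three scheduled post-baseline readings per period: Day 1 post-injection, Day 4 and Day 29 pre-injection; then Day 29 post-injection, Day 32 and Day 57 (Protocol Table 1).
- Safety Set: at least one injection received (SAP 5.2), so people who leave before Injection 2 stay in the table.
- d, the share leaving before Injection 2: not given. SAP 4.2 assumes about 10% excluded from the Evaluable Set for any reason, so 0% to 10% is assumed here.
- v and b, the per-period probabilities of a given worst grade after vaccine and after placebo: not given. Illustrative values are used.

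**Formulas for the Day 1-baseline worst result**

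- Sequence 1 = (1 − d)[1 − (1 − v)(1 − b)] + d·v
- Sequence 2 = (1 − d)[1 − (1 − b)(1 − v)] + d·b
- Difference = d(v − b)

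The product form assumes independent periods. The cancellation at d = 0 does not need this, because within-person correlation acts equally in both sequences.

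**Results (no period effect, no carry-over)**

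| v | b | d | Seq 1 | Seq 2 | Difference | Period 1 alone |
|---|---|---|---|---|---|---|
| 3% | 1% | 0% | 3.97% | 3.97% | 0 | 2 points |
| 3% | 1% | 10% | 3.87% | 3.67% | 0.2 points | 2 points |
| 15% | 5% | 0% | 19.25% | 19.25% | 0 | 10 points |
| 15% | 5% | 5% | 19.04% | 18.54% | 0.5 points | 10 points |
| 15% | 5% | 10% | 18.83% | 17.83% | 1.0 point | 10 points |
| 30% | 5% | 10% | 33.15% | 30.65% | 2.5 points | 25 points |

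Second row: 0.9 × 3.97% + 0.1 × 3% = 3.87%, and 0.9 × 3.97% + 0.1 × 1% = 3.67%.

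**Relaxing the assumptions**

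- Period effect: suppose Period 2 rates are 0.8 times those of Period 1, with d = 0, v = 15% and b = 5%. Sequence 1 is 1 − 0.85 × 0.96 = 18.4% and Sequence 2 is 1 − 0.95 × 0.88 = 16.4%, a difference of 2.0 points.
- Simulation with correlated within-person values, three readings per period and a 1 SD vaccine effect: the difference is about 0.1 point at d = 0 (simulation noise), 2.0 points at d = 10%, and 2.1 points at d = 0 with a 0.2 SD carry-over. The Day 29-baseline worst result shows about 19 points when there is no carry-over.

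**Do the other tables fill the gap?** The per-visit tables show Period 1 by product, but separate visit tables do not give each participant's worst grade. They can also miss readings. SAP Appendix B uses an unscheduled assessment only when the scheduled one is absent, while SAP 6.1 brings unscheduled values into maximum and minimum on-treatment values for safety. A high unscheduled reading in Period 1 could therefore enter only the worst-result summary, which is the one that mixes products.

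**The case against.** The strongest reply is that the same paragraph already covers most of the ground.

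- At all three scheduled Period 1 readings Sequence 1 has had only vaccine and Sequence 2 only placebo, so the per-visit shifts are uncontaminated there.
- The Day 29 repeat is itself a worst-grade contrast of placebo (Sequence 1) with vaccine (Sequence 2), and with v = 15% and b = 5% it shows the 10-point effect in full.
- Participants with Grade 2 or higher abnormalities are listed with all their vital-sign results, so each event can be traced to the preceding injection.
- No between-sequence difference or interval is planned for vital signs, and a whole-study worst grade is a legitimate descriptive summary.
- SAP section 1 says that the SAP prevails where it differs from the protocol.

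All of this stands, and it limits the point. It does not close it. The listing gives cases, not rates by product. The per-visit tables are not a per-participant worst grade. Precedence of the SAP does not explain a departure that section 7 says does not exist.

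Two stronger readings are tempting and are not supported. A reader might infer that the sequence difference is zero whatever the vaccine does. That needs full receipt of both injections, no period effect and no carry-over. The Safety Set keeps one-injection participants, and the documents' no-carry-over argument concerns troponin, not vital signs. A reader might also infer that this table is the one intended to detect vaccine-related abnormalities. The SAP gives it no such purpose; the only purpose stated in that paragraph belongs to the Day 29 repeat.

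**Conclusion.** The point holds in a limited form. The Day 1-baseline worst-grade shift is unbounded at Injection 2, mixes both products in each sequence column, and loses most or all of the vaccine-placebo contrast. From attrition alone, the contrast that remains is d times the true difference, at most a tenth of it at d = 10%. A period effect or carry-over would also move the difference, by an amount the table cannot separate from a vaccine effect. No worst-grade summary is specified from post-Injection 1 to pre-Injection 2, which departs from the presentation in Protocol 9.4.2.

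The sizes rest on assumed vital-sign rates, attrition, period effect and carry-over. The structure does not, apart from the plain reading that an unqualified worst post-baseline result runs to the end of the study. Severity is the lowest: vital signs are descriptive, they are not a primary, secondary or exploratory endpoint, and no conclusion on cTnI changes.

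**What to change.** In SAP 6.4.3:

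- Define the Day 1-baseline worst result as the worst from post-Injection 1 to pre-Injection 2, and the Day 29-baseline worst result as the worst from post-Injection 2 to EOS.
- Label each column with the product received in that interval.
- If a whole-study worst value is wanted, keep it as a supplementary descriptive summary labelled as covering both products.

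This restores the by-intervention, by-injection presentation of Protocol 9.4.2. The cost is a sentence or two of SAP text, one date cut in a derivation, and relabelled table columns. No new data are needed.
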